### 3.3.4 Withdrawal of patients from therapy or assessments

Patients may potentially be withdrawn from trial treatment or from the trial as a whole (“withdrawal of consent”) with very different implications, please see [Sections 3.3.4.1](#) and [3.3.4.2](#) below.

Every effort should be made to keep the randomised patients in the trial: if possible on treatment, or at least to collect important trial data.

Measures to control the withdrawal rate include careful patient selection, appropriate explanation of the trial requirements and procedures prior to randomization, as well as the explanation of the consequences of withdrawal.

The decision to withdraw from trial treatment or from the whole trial as well as the reason must be documented in the patient files and CRF.

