#### 3.3.4.1 Withdrawal from trial treatment

An individual patient is to be withdrawn from trial treatment if:

- The patient wants to withdraw from trial treatment, without the need to justify the decision.
- The patient needs to take concomitant drugs that interfere with the investigational product or other trial medication. Please refer to [Section 4.2.2](#) for restricted medication during this trial. The patient can no longer be treated with trial medication for other medical reasons (such as surgery, adverse events, other diseases, or pregnancy).
- If a hepatic injury alert (as defined in [Section 5.2.6.1](#)) is detected without identification of an alternative cause in the work-up according to the “DILI checklist”, discontinuation of treatment with study drug should be considered.
- The patient has repeatedly shown to be non-compliant with important trial procedures and, in the opinion of both, the investigator and sponsor representative, is not willing

or able to stick to the trial requirements in the future. For individual stopping rules related to specific adverse events, please see [Section 4.2.1](#) Other treatments and emergency procedures.

Patients who terminate study drug early should be encouraged to follow all study procedures per the [Flow Chart](#) until week 12, but not receive any more study drug at the respective visits. Given the patient's agreement, the patient will undergo the procedures for early treatment discontinuation and follow up as outlined in the [Flow Chart](#) (FC) and [Section 6.2.3](#). For all patients the reason for withdrawal from trial treatment (e.g. adverse events) must be recorded in the CRF. These data will be included in the trial database and reported.

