## 4.2 OTHER TREATMENTS, EMERGENCY PROCEDURES, RESTRICTIONS

### 4.2.1 Other treatments and emergency procedures

If the patient requires additional medical therapy or dose increase of baseline ulcerative colitis medication to treat the underlying ulcerative colitis due to disease worsening (cf. [Table 3.1.1](#) Study Definitions), the study drug must be discontinued and patients may receive conventional treatment for active disease. Such patients should stay in the trial but will be considered as treatment failures in the intent-to-treat (ITT) analysis.

If infusion or anaphylactic reaction had already occurred in the very same patient in the past, pre-treatment with steroids before next IMP administration is permitted as secondary prophylaxis.

Systemic steroids dosed intravenously or orally for less than 24 hours as treatment of infusion or anaphylactic reactions are permitted and do not lead to treatment discontinuation nor to assignment as treatment failures in the ITT analysis.

Management of Adverse Events:

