Malignant tumours	(SMQ “Malignancies” – not for display) (Sub-SMQ “Malignant or unspecified tumours” – not for display) Narrow Sub-SMQ “Malignant tumours” Sub-SMQ “Haematological malignant tumours” Sub-SMQ “Non-Haematological malignant tumours”

Based on the specification provided in ICH E3 (17), the sponsor has defined AEs which are to be classified as ‘other significant’. For the current trial, these will include those non-serious AEs which were reported with ‘action taken = Drug Withdrawn’ or ‘action taken = Dose Reduced’.

The exposure-adjusted incidence rate and frequency of patients with AEs will be summarised by treatment, primary system organ class and preferred term. AEs which were considered by the investigator to be drug related will be summarised separately. Separate tables will also be provided for patients with SAEs, patients with drug-related AEs, patients with investigator-reported AESIs, patients with AE leading to discontinuation of the trial, patients with other significant AEs and User-defined Adverse Event Concepts (UDAEC) (see [Table 7.8.1: 1](#)). AEs will also be summarized by maximum intensity based on the RCTC measure (see [Section 5.4.1](#)).

For disclosure of AE data on ClinicalTrials.gov, the frequency of patients with non-serious AEs occurring with an incidence of greater than 5% (in preferred terms) will be summarised by treatment, primary system organ class and preferred term. The frequency of patients with SAEs will also be summarised.

For disclosure of AE data in the EudraCT register, the frequency of non-serious AEs with an incidence of greater than 5 % (in preferred terms) and the frequency of SAEs will be summarised.

7.8.2 **Laboratory data**

The analyses of laboratory data will be descriptive in nature and will be based on BI standards (18). Note that data from the central laboratory will be used for all displays described below, unless otherwise specified.

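### No AE table named in SAP 7.8.1 shows all AEs that stopped study drug, so a serious AE that ends treatment in a patient who stays in the trial is not identified as such

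*SAP*

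**What the plan says.** SAP 7.8.1 begins its list of additional AE tables with "Separate tables will also be provided for patients with SAEs, patients with drug-related AEs". It continues with investigator-reported AESIs, "patients with AE leading to discontinuation of the trial", other significant AEs and the user-defined AE concepts. The 'other significant' class is defined just before that list: "For the current trial, these will include those non-serious AEs which were reported with" an action taken of drug withdrawn ("action taken = Drug Withdrawn") or dose reduced.

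Protocol 3.3.4 draws the distinction that matters here: "Patients may potentially be withdrawn from trial treatment or from the trial as a whole". For those who stop treatment, Protocol 3.3.4.1 says: "Patients who terminate study drug early should be encouraged to follow all study procedures per the" Flow Chart until week 12, off drug. Protocol 4.2.1 says of patients taken off drug because worsening UC needs further therapy: "Such patients should stay in the trial but will be considered as treatment failures in the intent-to-treat (ITT) analysis".

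At patient level, SAP 6.6.1 reports the reasons for withdrawal from treatment as entered on the eCRF. The disposition summary in SAP 7 counts premature discontinuations by reason.

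**The concern.** AEs that lead to stopping study drug, by arm and preferred term, are a basic measure of tolerability. Part 1 has the stated aim of identifying safe as well as efficacious regimens (Protocol 2.1.1), so a reader comparing the three doses with placebo would look for that table.

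The SAP keys its table to leaving the trial instead. In a design that tries to keep patients after they stop drug, these are different sets of events. The class that does use the drug-withdrawn flag excludes serious events, which matter most for tolerability.

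The protocol itself creates such cases. Malignancies are always classed as serious (5.2.6.1) and, with named exceptions, are a reason to stop drug (4.2.1). Worsening of UC is recorded as an AE (5.2.6.2), becomes serious if it leads to hospitalisation, and stops drug if further UC therapy is needed, while the patient is meant to stay. This last route could plausibly differ in frequency between placebo and active arms, so the missing identification need not be balanced across arms.

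**Working it through.** The plan gives no figure to reproduce. The check sorts every AE that stops study drug by seriousness and by whether the patient leaves the trial because of it, and matches each cell to the tables named in SAP 7.8.1.

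| Drug-stopping AE | Count | SAE table | Trial-discontinuation table | 'Other significant' table |
|---|---|---|---|---|
| Non-serious, patient stays | a | no | no | yes |
| Non-serious, patient leaves | b | no | yes | yes |
| Serious, patient leaves | c | yes | yes | no |
| Serious, patient stays | d | yes | no | no |

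Let e be the number of serious AEs that did not stop drug. Take one arm and one preferred term, with at most one such event per patient for simplicity.

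- Wanted: a + b + c + d.
- 'Other significant' table: a + b. The class also admits dose reductions, but Protocol 4.1.4 permits no dose modification, so it amounts to non-serious AEs with drug withdrawn.
- Trial-discontinuation table: b + c, plus any AE that ended participation without having stopped drug.
- SAE table: c + d + e.

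The tables for drug-related AEs, AESIs and user-defined concepts may repeat some of these events, but they are not selected on action taken with study drug. In the SAE table, d is mixed with e and nothing separates them. In the other two tables d does not appear. So a + b + c + d cannot be recovered by preferred term from the named tables, and d is the part that is never identified as drug-stopping.

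The patient level is different. The planned counts by reason should give, for each arm, the number who stopped because of an AE, whether serious or not. Under the one-event simplification this is a + b + c + d summed over all terms. What is missing is the breakdown by system organ class, preferred term and seriousness.

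**The case against.** The strongest reply is that the list in SAP 7.8.1 may not be complete. Protocol 7.3.5 promises the sponsor's standard tables and listings, SAP 7.8 follows sponsor standards, and SAP 7.8.1 refers to sponsor guidance for details of AE summaries. The overall AE summary is also described in open terms. Any of these could contain a table of AEs leading to drug discontinuation, and the word 'trial' in the listed table could be loose wording for trial drug. The documents settle neither point. This part of the objection stands: the point can be made only about the tables that the SAP names.

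A reader might also infer that drug-stopping SAEs go unreported, or that the discontinuation rate is understated. The documents do not support either reading. Every such event is in the SAE table, and SAP 7 lists the individual values of all patients, so cases can be traced. Anaphylaxis and hepatic injury are tabulated as AESIs and malignancy as a user-defined concept. The by-arm count of patients who stopped for an AE does not depend on seriousness. The SAP does not present the 'other significant' table as a discontinuation rate, so its restriction to non-serious events is not an error in that table.

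Staying in the trial is encouraged, not guaranteed. A serious AE that also ends participation does reach the trial-discontinuation table; only cell d is affected.

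Finally, about 40 patients per arm were planned and the trial was terminated early, so there may be few such cases. That limits the practical weight but does not make the selection rule right.

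**Conclusion.** The point holds for the AE tables that SAP 7.8.1 names. None shows all AEs leading to discontinuation of study drug, and a serious AE that stops drug in a patient who stays is counted as an SAE without being identified as drug-stopping. The loss is the event-level comparison between arms, not the patient count and not the events themselves.

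The number of events affected cannot be derived from the documents. The conclusion assumes that 'discontinuation of the trial' means what it says and that the sponsor standards do not already supply the table. If either assumption fails, the remedy reduces to correcting a phrase or adding a cross-reference.

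This is a minor reporting point. Safety analysis is descriptive with no hypothesis testing, and nothing in efficacy, type I error or data collection depends on it. It is still worth correcting, because followed literally the rule selects the wrong events for a tolerability comparison by dose.

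**What to change.** In SAP 7.8.1, change the table's selection from AEs leading to discontinuation of the trial to AEs leading to discontinuation of trial drug, defined as action taken Drug Withdrawn, serious and non-serious together. Present it by arm, system organ class and preferred term. If a table of AEs leading to withdrawal from the trial is also wanted, keep it as a separate display under its own name. The 'other significant' class can stay as it is.

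The cost is one changed phrase and a changed selection in a table that is already planned. SAP 7.8.1 already uses the action-taken field, and Protocol 3.3.4.1 requires the reason for stopping treatment in the CRF, so no new data are needed.

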7.8.3 Vital signs

The analyses of vital signs (blood pressure, pulse rate, body temperature, and body weight, respiration rate) will be descriptive in nature.

Descriptive statistics of vital signs over time and for the difference from baseline (see [Section 6.7](#)) will be provided by treatment and will include the last value during on-treatment period, the minimum value during on-treatment period, and the maximum value during on-treatment period (see [Table 6.1: 1](#) for definition of the on-treatment period). Graphical displays via box

[figure not shown]
plots will be produced for the change from baseline, over time, for each continuous vital sign endpoint.

Clinically relevant findings in vital signs data will be reported as baseline conditions (at screening) or as AEs (during the trial) if judged clinically relevant by the investigator, and will be analysed as such.

7.8.4 ECG

Abnormal findings in 12-lead ECG will be reported as baseline conditions (at screening) or as AEs (during the trial) if judged clinically relevant by the investigator, and will be analysed as such.

No separate listing or analysis of ECG data will be prepared.

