	
Secondary endpoint (incl. in statistical testing strategy; Part 2 only)
 
Change in IBDQ score from baseline at week 12
 
Proportion of patients with combined Mucosal healing and histologic remission at week 12
 
(defined as mESS <math>\leq</math> 1 and Robarts Histology Index <math>\leq</math> 6)

Safety criteria:
	
Physical examination, vital signs, 12-lead Electrocardiogram (ECG), laboratory tests, adverse events, serious adverse events and tolerability. The intensity grading of AEs and abnormal laboratory values will be performed according to Rheumatology Common Toxicity Criteria (RCTC) Version 2.0.

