### 5.2 ASSESSMENT OF SAFETY

Safety will be assessed descriptively based on:

- Adverse events
- Serious adverse events (SAEs)
- Clinical laboratory values (haematology, clinical chemistry, coagulation and urinalysis)
- Intensity of adverse events will be assessed by Rheumatology Common Toxicity Criteria (RCTC) version 2.0 (refer to ISF for details)
- Physical examination
- Vital signs
- 12-lead ECG

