## 5.2.4 Electrocardiogram

The 12-lead ECGs will be recorded as scheduled in the flowchart. The investigator or a designee will evaluate whether the ECG is normal or abnormal and whether it is clinically relevant, if abnormal. ECGs may be repeated for quality reasons and the repeated recording used for analysis.

Additional ECGs may be recorded for safety reasons. Dated and signed printouts of ECG with findings should be documented in patient's medical record.

Clinically relevant abnormal findings will be reported either as baseline condition (if identified at the screening visit) or otherwise as adverse events and will be followed up and/or treated as medically appropriate.

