### **7.3.5 Safety analyses**

Adverse events will be coded using the current version of Medical Dictionary for Regulatory Activities (MedDRA) coding dictionary. Standard BI summary tables and listings will be produced.

All treated patients will be included in the safety analysis. In general, safety analyses will be descriptive in nature and will be based on BI standards. No hypothesis testing is planned.

Statistical analysis and reporting of adverse events will concentrate on treatment-emergent adverse events. To this end, all adverse events occurring between start of treatment and end of the residual effect period will be considered ‘treatment-emergent’. The residual effect

period (REP) is defined as 16 weeks after the last dose of trial medication. Adverse events that start before first drug intake and deteriorate under treatment will also be considered as 'treatment-emergent'. The primary set of safety outputs will be done including data through the first 12 weeks of treatment (consistent with the timing of the primary efficacy analysis); further outputs will be also produced which include all safety data through the REP.

Frequency, severity, and causal relationship of adverse events will be tabulated by system organ class and preferred term after coding according to the current version of the Medical Dictionary for Drug Regulatory Activities (MedDRA).

Laboratory data will be analysed both quantitatively as well as qualitatively. The latter will be done via comparison of laboratory data to their reference ranges. Values outside the reference range as well as values defined as clinically relevant will be highlighted in the listings. Treatment groups will be compared descriptively with regard to distribution parameters as well as with regard to frequency and percentage of patients with abnormal values or clinically relevant abnormal values.

Vital signs, physical examinations, or other safety-relevant data observed at screening, baseline, during the course of the trial and at the end-of-trial evaluation will be assessed with regard to possible changes compared to findings before start of treatment.

Immunogenicity data will be analysed in a descriptive way.

[figure not shown]
#### Pooled Analyses of Parts 1 and 2

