The individual values of all patients will be listed, including those collected during the off treatment period. Listings will generally be sorted by country, centre number, patient number and visit (if visit is applicable in the respective listing). AE listings will be sorted by treatment (see [Section 7.8.1](#) for details).

The following standard descriptive statistical parameters will be displayed in summary tables for continuous variables:

N	number of non-missing observations
Mean	arithmetic mean
SD	standard deviation
Min	minimum
Q1	lower quartile
Median	median
Q3	upper quartile
Max	maximum

Statistical parameters will be displayed to a defined number of decimal places as specified in the BI guideline "Reporting of clinical trials and project summaries" (9).

Tabulations of frequencies for categorical data will include all possible categories and will display the number of observations in a category as well as the percentage (%) relative to the respective treatment group (unless otherwise specified, all patients in the respective patient set whether they have non-missing values or not). Percentages will be rounded to one decimal place. The category missing will be displayed only if there are actually missing values.

Due to the long REP, i.e., 16 weeks after last treatment, there will be no off-treatment data available at the time of the primary analysis at Week 12. Listings of data presented by-visit, which include both on- and off-treatment data, will be produced at the time of the updated analysis after final DBL (see also [Section 6.7](#)).

[figure not shown]
Disposition of the patient population participating in the trial will be summarised by presentation of the frequency of patients screened, entered, screened but not entered, treated, entered but not treated, who completed all doses of trial medication as planned, who completed the PE visit (EOT), who completed the trial (EOS), and who were prematurely discontinued, by reason. Disposition will also be summarized and listed by country. The frequency of patients with iPDs will be presented for the RS by treatment. The iPDs will be listed per patient indicating whether or not the iPD led to exclusion from patient sets analyzed.

The frequency of patients in each of the different analysis sets will also be presented by treatment.

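### SAP 7.8.4 reports ECG only through findings judged clinically relevant, so a by-dose excess of new abnormalities below that threshold would appear in no planned output

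*SAP*

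**What the plan says.** The protocol synopsis gives the safety criteria as "Physical examination, vital signs, 12-lead Electrocardiogram (ECG), laboratory tests, adverse events, serious adverse events and tolerability", with ECG and adverse events as separate items. Protocol 5.2 opens with "Safety will be assessed descriptively based on" and ends its list with the 12-lead ECG. In the Part 1 flow chart, ECGs fall at V1a, V2, V4, V5 and EOS, and none is marked at V6.

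Protocol 5.2.4 has the investigator or a designee call each ECG normal or abnormal and, if abnormal, clinically relevant or not. It sends clinically relevant abnormal findings to baseline conditions or AEs. It also says: "ECGs may be repeated for quality reasons and the repeated recording used for analysis".

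Protocol 7.3.5 covers change from the pre-treatment state. Vital signs and physical examinations are named, and the sentence then widens to cover everything else: "other safety-relevant data observed at screening, baseline, during the course of the trial and at the end-of-trial evaluation will be assessed". ECG is not named there.

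SAP 7.8.4 has two elements. The first is the reporting route: "Abnormal findings in 12-lead ECG will be reported as baseline conditions (at screening) or as AEs (during the trial) if judged clinically relevant". The judgement is the investigator's, and such findings enter the baseline-condition and AE analyses. The second is "No separate listing or analysis of ECG data will be prepared". The General Remarks in SAP section 7 say: "The individual values of all patients will be listed, including those collected during the off treatment period".

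**The concern.** The AE route works one patient and one judgement at a time. An ECG that is newly abnormal, but that the investigator considers unimportant for that patient, generates no AE. Whether such changes are more frequent on active drug than on placebo, or rise with dose, is a group-level question. The randomised placebo arm, the three active regimens and the pre-treatment ECG can answer it, and individual relevance judgements cannot.

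What is at stake is the safety statement in the trial report. ECG would be described as an assessed safety parameter, when for findings below the relevance threshold no comparison had been made.

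**Working it through.** The documents give no figure for this point to reproduce. The check is mainly a side-by-side reading, plus a count.

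**Step 1: which ECG results reach an output.**

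- *Abnormal and clinically relevant:* recorded as a baseline condition or AE (protocol 5.2.4, protocol 5.2.6.2 and SAP 7.8.4). For AEs, SAP 7.8.1 then applies: "The exposure-adjusted incidence rate and frequency of patients with AEs will be summarised by treatment, primary system organ class and preferred term". These findings are visible by arm.
- *Abnormal and not clinically relevant:* no AE, no ECG table and no ECG listing. These findings are visible nowhere in the planned outputs.
- *Normal:* also not tabulated, so no denominator of evaluated ECGs is shown by arm and visit.

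**Step 2: comparison with the other safety measurements in the SAP.**

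| Measurement | Relevant findings go to baseline conditions or AEs | Also a descriptive display |
|---|---|---|
| Laboratory data (7.8.2) | yes | yes: by-visit statistics, change from baseline, shift tables |
| Vital signs (7.8.3) | yes | yes: by-visit statistics and change from baseline, by treatment |
| ECG (7.8.4) | yes | no |

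Elsewhere in the SAP the AE route supplements a descriptive display. For ECG it replaces one, and the visible text gives no reason.

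**Step 3: consistency within the SAP.** The General Remarks promise a listing of all patients' individual values and name no exception. SAP 7.8.4 says that no separate ECG listing will be made. The two statements conflict unless 7.8.4 is read as overriding the general rule.

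**Step 4: size.** Inputs are 160 planned patients (protocol 3.1.1) and the flow-chart visits.

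- V2, V4 and V5: 160 × 3 = 480 scheduled ECGs.
- V4 and V5 only, after the first dose: 160 × 2 = 320.
- EOS adds further ECGs for patients who do not roll over.

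Both counts are upper bounds. They assume full attendance, and SAP section 3 records early termination.

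**Step 5: illustration with assumed numbers.** Suppose new abnormal ECGs occur in 2/40 = 5% on placebo and 8/40 = 20% on 1200 mg. Let *s* be the share judged not clinically relevant, taken as equal in both arms. The number visible in AE tables is (1 − *s*) times the count.

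- *s* = 0: 2/40 against 8/40. The whole difference is visible.
- *s* = 0.5: 1/40 = 2.5% against 4/40 = 10%. Half of it is visible.
- *s* = 1: 0/40 against 0/40. Nothing is visible.

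The loss depends wholly on *s*, which the documents do not give.

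**The case against.** The strongest reply is that SAP 7.8.4 follows the protocol. Protocol 5.2.4, the section specific to ECG, sets the same baseline-condition and AE route. Protocol 5.2.6.2 likewise has ECG changes recorded as AEs when the investigator judges them clinically relevant. Protocol 7.3.5 does not name ECG and prescribes no display. Descriptive AE tables by arm could be said to satisfy protocol 5.2. This stands to the extent that the SAP does not plainly contradict the protocol. The comparison with pre-treatment ECGs is an inference from the general phrase in 7.3.5. It does not fully meet the point, because protocol 5.2 and the synopsis list ECG beside adverse events, and 5.2.4 provides for choosing a recording for analysis.

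A reader might also infer that the SAP bars all ECG analysis, or that a treatment-related ECG shift could not be seen at all. The documents do not support either reading. The SAP excludes a *separate* listing or analysis, and a rise in clinically relevant ECG findings can show in the AE tables by treatment.

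Other replies carry some weight. Protocol 1.1 reports no clinically relevant ECG changes in the healthy-volunteer trials, and the risk table in 1.4 names no cardiac risk; this keeps the point moderate, although those volunteers were not patients with ulcerative colitis. The DMC reviews unblinded safety data (protocol 7.4), which protects patients during the trial but adds no comparison to the planned SAP outputs. A programmer would probably follow 7.8.4 over the general listing rule, so that conflict is mainly one of wording.

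Two limits are real. Protocol 5.2.4 requires ECG printouts in the medical record but does not say that each evaluation is entered in the database. The body of SAP section 4, on changes to the planned analysis, is not visible, and the safety endpoint list in SAP 5.4.1 is incomplete in the text available. A declared change therefore cannot be excluded.

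**Conclusion.** The concern holds in a limited form. SAP 7.8.4 confines ECG output to findings the investigator judges clinically relevant. That matches the protocol's reporting route. It falls short of the descriptive ECG assessment in protocol 5.2 and, by inference, of the comparison with pre-treatment findings in 7.3.5. It also conflicts with the SAP's own general listing rule.

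The practical loss is specific: an excess by dose of new abnormalities below the relevance threshold would appear in no planned output. It concerns at most 320 scheduled ECGs at V4 and V5, plus EOS. The documents report no ECG signal, so this is a gap in what the trial can say about ECG safety and is not evidence of a missed harm.

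The verdict rests on the visible SAP text. Whether the recommended table can be built depends on the evaluation required by protocol 5.2.4 having been captured.

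**What to change.** Replace the last sentence of SAP 7.8.4 with wording such as:

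> *For the SAF, a shift table by treatment will show the investigator's ECG evaluation (normal; abnormal, not clinically relevant; abnormal, clinically relevant) from the last ECG before the first dose to V4, V5 and the worst evaluation after the first dose. EOS will be added at the final lock. Patients with any abnormal ECG after the first dose will be listed.*

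The baseline definition in SAP 6.7 can be used unchanged. State as well how the abnormal-only listing relates to the all-values rule in the General Remarks.

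If the evaluations are not in the database, 7.8.4 should say so and state that ECG was assessed only through AEs, and the General Remarks should name ECG as an exception. The report should then not claim a descriptive ECG comparison.

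The cost is one table, one listing and the SAP wording. If the data are held, no new visit, procedure or reader is needed. If they are not, the change is to wording only.
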